5. HYPOTHESIS OF THE STUDY

Opening of the transverse carpal ligament percutaneously ultrasound-guided for the surgical treatment of carpal tunnel syndrome (CTS) has better results than opening by open surgery (palmar incision).

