6. SPECIFIC AND SECONDARY OBJECTIVES OF THE STUDY

Main objective:

To analyze the functional results of the surgical treatment of CTS using percutaneous ultrasound-guided technique and to compare them with the results obtained by open surgery with a palmar incision.

Secondary objective:

To analyze the presence of complications (scar pain, pillar pain) and the pre- and postoperative difference in manual grip strength (measured with a JAMAR manual dynamometer) of surgical treatment of CTS using percutaneous ultrasound-guided technique and compare them with the results obtained by open surgery with a palmar incision.

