These two forms of surgical treatment are approved and used in our Service. The assignment to one or another surgical technique will be made based on the criteria of the physician who diagnoses the patient, as he or she does in his or her usual clinical practice, once the patient's clinical characteristics, pathology, and preferences have been heard.

Data will be collected from the patients included in the study in the preoperative consultation, intraoperatively and in the revision consultations that are usually carried out for this pathology 2 weeks after surgery, 6 weeks and 3 months.

In the preoperative consultation, the following will be collected:

- 1.- Grip strength of the hand measured with JAMAR manual dynamometer.
- 2.- Score of the specific questionnaire for the pathology of CTS: Boston Carpal Tunnel Syndrome Questionnaire²² (ANNEX 1).

Surgery will include:

- 1.- Time of surgical intervention
- 2.- Use or not of an ischemia cuff to perform surgery.

In the 2-week postoperative consultation, the following will be assessed:

- 1.- State of surgical wound.
- 2.- Presence of skin infection or other complication.
- 3.- Presence of pillar pain.
- 4.- Absence or presence of CTS (paresthesias or pain in the territory of the median nerve).

In the consultations that will be carried out 6 weeks and 3 months after surgery, the following will be assessed:

- 1.- Surgical incision status.
- 2.- Presence of skin infection or other complication.
- 3.- Presence of pillar pain.
- 4.- Absence or presence of CTS (paresthesias or pain in the territory of the median nerve)
- 5.- Grip strength of the hand measured with a JAMAR manual dynamometer.
- 6.- Score of the specific questionnaire for the pathology of CTS: Boston Carpal Tunnel Syndrome Questionnaire²² (ANNEX 1).

Data recording and management.

Potential candidates who meet the main characteristic of the study will be offered informed consent. Once the consent has been signed, a list of patients who meet the inclusion criteria and none of the exclusion criteria will be created.

The principal investigator ([name] [name]) will be responsible for the collection and custody of the data and will ensure that the pseudonymisation of the participants is maintained. These will be identified through a code in the CRD and in the electronic database, all their information being associated with this code and not with their personal data.

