The other members of the team as third parties involved in the statistical analysis of the data will only have access to the coded information.

Statistical analysis.

A descriptive analysis of the data will be carried out, presenting the qualitative variables with their absolute frequency and percentage, and the quantitative variables with their mean and standard deviation (SD) or median and percentiles if they do not conform to a normal distribution.

Initially, a univariate analysis will be performed to determine which variables could have an independent effect on functional outcomes (grip strength, and the validated questionnaire for CTS: Boston Carpal Tunnel Syndrome Questionnaire ²²).

To compare quantitative variables between the two groups, to assess whether there are differences and whether they are significant, the normality of the distribution of the data in each of the cohorts will be analysed and the parametric t-student test or the

non-parametric test (Mann-Whitney U) will be applied. For the comparison of the qualitative variables between the two cohorts, the Chi-square test will be used.

Subsequently, including as independent variables those that show significance in the univariate analysis or are of clinical interest, they will be included in multivariate regression models.

The data will be analyzed with the SPSS 22.0 Software and 0.05 will be considered as the α accepted significance level for all hypothesis tests.

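### Technique is chosen by the physician, but the only between-group significance tests named are unadjusted, and the planned regression is not tied to the main objective

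*Protocol*

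**What the plan says.** The study is an observational cohort. Under Procedure in section 7, "The assignment to one or another surgical technique will be made based on the criteria of the physician who diagnoses the patient", once the patient's "clinical characteristics, pathology, and preferences have been heard". The hypothesis (section 5) is that the percutaneous technique "has better results than opening by open surgery", and the main objective (section 6) is to analyse its functional results and "to compare them with the results obtained by open surgery with a palmar incision".

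The Statistical analysis text in section 7 sets out three steps:

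- A univariate analysis to find "which variables could have an independent effect on functional outcomes", these outcomes being grip strength and the BCTQ.
- Two-group tests. "To compare quantitative variables between the two groups, to assess whether there are differences and whether they are significant", normality is checked and Student's t or Mann-Whitney U is applied. Qualitative variables get a Chi-square test.
- After that, "those that show significance in the univariate analysis or are of clinical interest, they will be included in multivariate regression models".

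The preoperative visit already records grip strength and the "Score of the specific questionnaire for the pathology of CTS: Boston Carpal Tunnel Syndrome Questionnaire".

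**The concern.** When patient features steer the choice of technique, a difference after surgery mixes the effect of technique with differences that were there beforehand. The protocol says that features do steer it. Yet the only procedures it names for judging whether a group difference is significant ignore the preoperative state. BCTQ is a quantitative variable and the primary endpoint, so it falls under that sentence.

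The regression that follows could repair this, but the text does not commit it to doing so. It does not say that technique and preoperative BCTQ are always in the model, or that the adjusted estimate answers the main objective. The entry rule is a lesser weakness: a confounder that differs between groups can miss univariate significance and be left out, although preoperative BCTQ would seldom be lost that way. The phrase about an independent effect is only a supporting point. A univariate test cannot show independence, but the wording describes a screen for candidates.

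At stake is a claim of superiority resting on a p-value that partly reflects who was offered which operation.

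**Working it through.** **Inputs from the protocol (section 7, Sample size calculation).** SD 1; two-sided alpha 0.05; planned difference 0.94; 98 per group; 10% loss. I take 98 × 0.9 ≈ 88 evaluable per group. The protocol gives no figure for confounding, so there is none to reproduce. Its 98 does not follow from 0.94 and SD 1, which give 18 per group, or 20 with loss. That is a separate matter; 98 is used here only as the planned size.

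**Assumed, not in the document.** Correlation between preoperative and follow-up score r = 0.5; preoperative gap d = 0.3 or 0.5 points; no technique effect; how the gap evolves.

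**Smallest significant difference.** Standard error = √(2/88) = 0.151. The critical value on 174 df is 1.974, and 1.974 × 0.151 = 0.298. An observed difference of about 0.30, a third of 0.94 (0.298/0.94 = 0.32), reaches p < 0.05.

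**Model.** With g = 1 for one group and 0 for the other, preoperative score = z + d·g and follow-up score = L·d·g + r·z + √(1−r²)·e, where z and e are independent standard normal. L = r means that scores regress to a common mean; L = 1 means that the gap is stable. With no technique effect, the expected group differences are:

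- follow-up score, unadjusted: L·d, SD 1
- change from baseline, unadjusted: (L−1)·d, SD √(2−2r) = 1 at r = 0.5
- baseline-adjusted regression: (L−r)·d, residual SD √(1−r²) = 0.866

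Example, L = 0.5 and d = 0.3: bias 0.5 × 0.3 = 0.15, noncentrality 0.15/0.151 = 0.995, rejection 16.7%. At d = 0.5: bias 0.25, noncentrality 1.658, rejection 37.8%.

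**False-positive rates, d = 0.3 / 0.5.** Noncentral t for the unadjusted tests in the first and third rows; simulation (20,000 replicates) for the adjusted column and all of the second row.

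| How the gap behaves | Follow-up score, unadjusted | Change, unadjusted | Baseline-adjusted |
|---|---|---|---|
| Regresses to a common mean (L = 0.5) | 16.7% / 37.8% | 16.7% / 37.8% (opposite direction) | 5.1% / 4.9% |
| Halfway (L = 0.75) | 31.7% / 70.2% | 7.7% / 12.8% | 8.7% / 15.8% |
| Stable (L = 1) | 50.8% / 91.0% | 5% / 5% | 19.9% / 45.1% |

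If the gap would widen by 30% without any technique effect (L = 1.3), the simulated rates are 72.8% / 99.0%, 9.2% / 17.0% and 43.9% / 83.9%.

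**Range.** For the unadjusted follow-up score with regression to a common mean, r from 0.3 to 0.6 and d from 0.2 to 0.5 give 6.8% to 50.8%.

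**No imbalance.** With d = 0 every method keeps 5%. Adjustment then only narrows the 95% CI half-width, from 0.298 to 1.974 × √(2 × 0.75/88) = 0.258.

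**The case against.** The strongest reply is that adjustment is already planned. The text moves from a univariate step to two-group tests to regression, a common layout for a cohort study, and nothing ranks the t-test as the main analysis. The sentence on quantitative variables can also serve baseline comparability, and the clinical-interest route can admit both technique and preoperative BCTQ. All of this stands. A reader might infer that the protocol ignores confounding, or that its conclusion will rest on the t-test; the document supports neither.

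Naming covariates is often left to an analysis plan, which is not shown. That also stands, so missing detail is not the complaint. What the protocol does fix is a set of unadjusted significance tests and an entry rule driven partly by significance, and both suit its own assignment method poorly.

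A further reply concerns the endpoint. The Summary (section 3) defines it as improvement, which may mean change from the preoperative score. Unadjusted change keeps its 5% rate under a stable gap, where the adjusted model does not, and it also does better than the adjusted model halfway and under a widening gap. This is correct. One might infer from the 51% / 91% figures that the planned analysis carries that error, or that adjustment cures it. Neither follows: the first depends on which score is compared and how the gap evolves, and the second fails in three of the four cases shown.

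**Conclusion.** The concern holds in limited form. In a comparison where the physician selects the technique, the only significance tests named for group differences are unadjusted, and the planned regression is not committed to estimating the technique effect. An unadjusted p-value could be reported as that effect.

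The document does not allow the size of the harm to be stated. The rates above rest on an assumed correlation, imbalance and course of the gap, and without imbalance there is no excess error. Baseline adjustment gives fewer false positives than the unadjusted follow-up comparison in every imbalanced case shown, but neither it nor change is best throughout. No loss of power is claimed: at r = 0.5, the lowest power of the unadjusted follow-up test for 0.94 points in the cases examined was 83.0%. The point is worth fixing because the key covariate is already collected. Confidence is moderate, since the text leaves room for a sound analysis.

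**What to change.** In the Statistical analysis text of section 7, state that:

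- The main objective is answered by the regression already planned, with postoperative BCTQ as outcome and with technique and preoperative BCTQ always in the model. Preoperative grip strength may be added, as it is already collected.
- Other covariates are chosen because they influence the choice of technique, not by univariate significance.
- The result is the adjusted mean difference with its 95% CI, worded as an adjusted association.
- The t, Mann-Whitney U and Chi-square comparisons are descriptive.
- Change in BCTQ from baseline is reported alongside as a sensitivity analysis. Its model leaves out the preoperative BCTQ term, because including it would return the same technique estimate as the main model.

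I would not require the two analyses to agree before a difference is stated. At a true 0.4 points with r = 0.5 and no imbalance, that rule cuts power from about 86% to 73%, and with a 0.5-point imbalance it can fall to 17%.

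Costs: re-evaluation by the ethics committee (section 8), reliance on linear-model assumptions, and a need to handle missing preoperative scores. The preoperative visit lists only BCTQ and grip strength, so any other driver of the choice must be recorded, or confounding by it remains.

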7. DESIGN AND METHODS

Design:

Prospective observational cohort study.

Study population:

Patients in the CHUVI Health Area who have been diagnosed with CTS by a specialist in Orthopaedic Surgery and Traumatology at that centre, have undergone surgery for this pathology from 1 January 2021 to 31 January 2024, and meet the inclusion and exclusion criteria.

- Inclusion Criteria:

- 1.- Patient diagnosed with CTS by clinical examination and confirmed by complementary test (Electromyogram).
- 2.- Patients over 18 years of age.
- 3.- Patients who belong to the CHUVI Health Area.
- 4.- Patients with the capacity to consent and who agree to participate by signing the informed consent.
- 5.- Follow the guidelines and reviews set forth in the Consultation.

- Exclusion Criteria:

- 1- Patient who has previously undergone surgery for the same pathology in the same hand (recurrence).
- 2.- Patient incapacitated or unable to follow guidelines indicated by the Physician.
- 3.- Patient with associated pathology in the same hand for which he/she is going to be operated on in the same surgical act.
- 4- Patients with the presence of associated synovitis at the level of the flexor tendons of the hand to be treated.

- Sample size calculation.

Based on the study published by Kim et al²³, who studied the minimum clinically important difference (MCID) for the Boston Carpal Tunnel Syndrome Questionnaire²², and accepting an alpha risk of 0.05 and a beta risk of less than 0.2 in a bilateral contrast,

98 subjects in the first group and 98 in the second group are needed to detect a difference equal to or greater than 0.94 units. The common standard deviation is assumed to be 1. A follow-up loss rate of 10% has been estimated.

Procedure

Patients from the CHUVI Health Area diagnosed with the explained pathology, who meet the inclusion and exclusion criteria, and who are going to undergo surgery at the CHUVI by specialist doctors from the Orthopaedic Surgery and Traumatology Service belonging to the Upper Limb Unit, will be recruited. These patients will be informed of their pathology, and after signing the informed consent, surgery will be performed in the two proposed ways:

-Procedure A: ultrasound-guided percutaneous surgery.

-Procedure B: open surgery through a short palmar incision.

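### The named two-sample tests use only patients scored at the tested visit and ignore their other BCTQ and grip scores, so outcome-related loss that follows a different pattern in each cohort can bias the comparison

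*Protocol*

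**What the plan says.** All the relevant text is in Protocol section 7.

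- **Collection (Procedure).** BCTQ and grip strength are taken at the preoperative consultation. They are taken again later: "In the consultations that will be carried out 6 weeks and 3 months after surgery, the following will be assessed", a list that includes both measures. The 2-week visit collects neither.
- **Expected loss (Sample size calculation).** "A follow-up loss rate of 10% has been estimated". The figure is not split by technique and is used only for the sample size.
- **Comparison (Statistical analysis).** Quantitative variables are compared by Student t if a normality check in each cohort allows it; otherwise a "non-parametric test (Mann-Whitney U) will be applied". Variables that are significant in the univariate step or of clinical interest come next: "they will be included in multivariate regression models". The type of regression, the form of the outcome and the visit are not given.

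The primary endpoint in the Summary is improvement on the BCTQ, with no visit attached.

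**The concern.** A two-sample test on the score at one visit, or on change to that visit, needs an observed value there. A patient who misses the 3-month review adds nothing to a 3-month comparison, even with baseline and 6-week scores on file. Ordinary regression on the 3-month score would drop the same patient, so the later regression step is not clearly a remedy.

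This matters in this design because technique is chosen by the physician after hearing the patient's preferences, and no blinding is described. Reasons for returning could therefore differ between the cohorts. If they do, and are linked to how patients are doing, part of the observed difference reflects who came back. The 6-week score carries some information about this, and the named tests do not use it.

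**Working it through.** **Inputs from the protocol.** 98 per cohort, SD 1, two-sided alpha 0.05, 10% loss, planning difference 0.94 (section 7, Sample size calculation). The protocol has no figure of its own for bias from loss.

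The 98 does not follow from its stated inputs: 2(1.96 + 0.842)²/0.94² = 17.8, so 18 per group, or 18/0.9 = 20 after loss. That is a separate matter; 98 serves here only as the cohort size.

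**Assumptions (not in the documents).** 6-week/3-month correlation 0.6; where loss is selective, its log-odds change by 1 per SD of the 6-week score; no true difference between cohorts.

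**Step 1: when bias arises.** Let p be the proportion lost in a cohort and g the mean of lost minus mean of retained patients. The retained mean equals the full mean minus p × g. For cohorts A and B,

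bias of the difference (A − B) = pB × gB − pA × gA.

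- Random loss: gA = gB = 0, so bias is 0, even if pA and pB differ.
- Same rate and same gap in both cohorts: bias is 0, even though loss is related to outcome.
- 5% v 15% loss with a gap of 0.5 in both: 0.15 × 0.5 − 0.05 × 0.5 = 0.05.

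**Step 2: size at 10% loss.** Averaging the assumed logistic loss curve over a standard normal 6-week score, with overall loss set to 10%, gives lost patients a mean of 0.817. Retained patients have −0.1 × 0.817/0.9 = −0.091. The 6-week gap is 0.908, so the 3-month gap is 0.6 × 0.908 = 0.545.

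- Selective in one cohort only: 0.10 × 0.545 = 0.054.
- Selective in opposite directions: 2 × 0.10 × 0.545 = 0.109.

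**Step 3: coverage.** Retained per cohort: 98 × 0.9 = 88.2, so SE = √(2/88.2) = 0.151. Coverage = Φ(1.96 − b/SE) − Φ(−1.96 − b/SE), where b is the bias.

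- b = 0.055: b/SE = 0.365, coverage 93.5%.
- b = 0.11: b/SE = 0.730, coverage 88.7%.

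**Step 4: simulation under the same assumptions.**

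| Scenario | Bias, attendees only | Coverage |
|---|---|---|
| Random, or alike in both cohorts | 0.00 | about 95% |
| 10%, selective in one cohort | 0.055 | 93.5% |
| 10%, opposite directions | 0.11 | 88% to 90% |
| 20%, opposite directions | 0.21 | about 74% to 75% |

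The last row is double the planned loss. An estimate that uses the 6-week score within each cohort has bias below 0.01 in every row, with practically the same standard error.

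**Step 5: when the remedy is weaker.** With about 10% loss in opposite directions:

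- If loss follows the 3-month state itself, the attendee-only bias is 0.18, and 0.12 remains after using the 6-week score.
- If half of the lost patients leave before 6 weeks, 0.11 falls only to 0.05.

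**The case against.** The strongest reply is that the protocol states no complete-case rule. Handling of missing scores is commonly left to a statistical analysis plan, which is not shown, and the regression step could be a repeated-measures model. This stands in part. Silence on missing data is not the point here; the point is that the test actually named cannot use a patient without the score at the tested visit. The open wording of the regression neither rules out nor promises a better method.

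A second reply is that the effect is small and hypothetical. At the planned loss, 0.055/0.94 is about 6% of the planning difference and 0.11/0.94 about 12%, and the mechanism is assumed. That also stands. The tests, however, are of zero difference, and coverage of 88% to 90% means a false-positive rate of 10% to 12% instead of 5%.

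Four stronger readings are tempting, and the documents do not support them:

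- That unequal loss between techniques is itself a bias. It is not; it must also be related to outcome.
- That the tests are unbiased only if loss is unrelated to outcome within each cohort. This is false, because selection that acts alike in both cancels from the difference (Step 1).
- That the 3-month comparison is the primary one. No visit is named.
- That inclusion criterion 5, on following the reviews, removes non-attenders. It can be read that way, but nothing says that an operated patient who misses a review is excluded.

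**Conclusion.** The point holds as a weakness in the chosen method, not as a demonstrated bias. The named tests discard scores that the protocol collects, while the protocol itself expects 10% loss. They can give a biased difference if loss is related to outcome and its pattern differs between cohorts.

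At 10% loss the size is about 0.05 units (selective in one cohort, coverage about 94%) to 0.11 units (opposite directions, coverage about 88% to 90%). These figures rest on SD 1 from the protocol and on an assumed correlation of 0.6 and dropout log-odds of 1 per SD. The protocol reports neither loss by technique nor the correlation between visits. With random loss, or loss that acts alike in both cohorts, the bias is zero. It is worth correcting because a better method needs only data already planned.

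**What to change.** In section 7, Statistical analysis, make the main between-cohort comparison of BCTQ, and likewise of grip strength, a linear mixed model of the 6-week and 3-month scores. Terms: technique, visit, technique by visit, baseline score, and the clinical covariates already intended for the regression step, with unstructured covariance across visits. State that every operated patient with at least one follow-up score is included. Report the technique difference at the primary visit, which the sponsor must name. Keep the t-test and Mann-Whitney U as descriptive or sensitivity analyses.

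The cost is analysis wording only: no new data or visits, mixed models are available in SPSS, and the simulations showed no loss of precision. The model assumes that loss is explained by the recorded scores, so the limits in Step 5 should be acknowledged. Patients lost before 6 weeks have no follow-up BCTQ and still drop out. The model does not by itself deal with confounding by choice of technique.

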4. BACKGROUND AND JUSTIFICATION OF THE STUDY

Surgical treatment for carpal tunnel syndrome consists of the transverse carpal ligament (LTC) section. The section of this ligament is usually done through a palmar skin incision. This technique is a common, simple, safe and effective procedure for the treatment of this pathology, but it is not exempt from complications such as the presence of painful palm scars, prolonged pain in the incision area, fatigue or weakness of the hand, periincisional pain (pillar pain) or prolonged convalescence time -return to previous activities⁻¹⁻³.

To try to minimize complications, percutaneous techniques have been developed. With these procedures, by not making an open incision through the palm, it is expected that the incidence of discomfort and tenderness in the palmar area will be reduced. In addition, it is also expected that there will be a decrease in postoperative morbidity, less time to return to work, and greater recovery of grip strength when this technique is used^{1,4-7}. However, its risk-benefit ratio compared to that of open release remains controversial⁸⁻¹². The risks to adjacent neurovascular structures inherent in these

percutaneous techniques remain one of the main factors preventing the acceptance of this technique^{4,13-15}.

To minimize these risks, ultrasound has been used as a guide when performing these percutaneous techniques, since ultrasound makes it possible to perfectly visualize carpal tunnel structures when performing this release^{1,12,16-18}. Ultrasound-guided percutaneous carpal tunnel release is a minimally invasive technique that has been developed over the last 20 years and has been shown to be effective and safe in several studies^{1,8,19-21}.

In our department, doctors from the Upper Limb Unit regularly use ultrasound for the diagnosis of upper limb pathology, as well as to perform local blocks when performing procedures under local anaesthesia. Due to the practice achieved with these procedures, ultrasound is being used as a support in other procedures such as the localization of foreign bodies, percutaneous release of CTS or the release of trigger fingers.

The aim of this study is to assess whether percutaneous release of the carpal tunnel guided by ultrasound provides, in our experience, more benefits than performing it through a short palmar incision.

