12.- ANNEX 1.- Validated Spanish version of the Boston Carpal Tunnel Syndrome Questionnaire²²

The following questions refer to the patient's symptoms on a typical day (24-hour period) during the past 2 weeks:

A. How severe is your wrist or hand pain at night?

1. I don't have pain in my wrist or hand
2. I have mild pain
3. I have moderate pain
4. I have severe pain
5. I have very severe pain

B. How often do you wake up during a typical night with wrist or hand pain (during the last 2 weeks)?

1. Never
2. Once
3. Two or three times
4. Four to five times
5. More than five times

C. Do you normally have pain in your hand or wrist during the day?

1. No
2. I have mild pain
3. I have moderate pain
4. I have severe pain
5. I have very severe pain

D. How often do you have pain in your wrist or hand during the day?

1. Never
2. Once or twice
3. Three to five times
4. More than five times
5. The pain is constant

E. How long did your last bout of pain last during the day?

1. I never have pain during the day
2. 10 minutes or less
3. 10-60 minutes
4. More than 60 minutes
5. The pain is constant throughout the day

F. Do you have numbness (loss of sensation) in your hand?

1. No
2. I have mild numbness
3. I have moderate numbness
4. I have severe numbness
5. I have very bad numbness

G. Do you have weakness in your hand or wrist?

1. No2. I have mild weakness3. I have moderate weakness4. I have severe weakness5. I have very serious weakness

H. Do you have a tingling sensation in your hand?

1. No2. I have mild tingling3. I have moderate tingling4. I have severe tingling5. I have very bad tingling

I. How serious is the numbness (loss of sensation) or tingling sensation at night?

1. I don't have numbness or tingling2. I have mild numbness or tingling3. I have moderate numbness or tingling4. I have severe numbness or tingling5. I have very bad numbness or tingling

J. How many times did you wake up during a typical night from numbness or tingling of the hand, in the last 2 weeks?

1. Never2. Once3. Two to three times4. Four to five times5. More than five times

K. Do you have difficulty grasping and using small objects such as keys or pens?

1. No2. I have mild difficulty3. I have moderate difficulty4. I have serious difficulty5. I have very serious difficulty

Please answer all answers by circling a number that you think is appropriate.

ACTIVITY	No difficulty	Little Difficulty	Moderate difficulty	Severe difficulty	I can't do anything because of the symptoms

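### The univariate covariate screen can admit variables recorded after the choice of technique, above all pillar pain, to the adjusted comparison of techniques

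*Protocol*

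**What the plan says.** The Statistical analysis part of section 7 sets two steps. A univariate analysis looks for variables related to grip strength and the Boston questionnaire (BCTQ). Multivariate models are then built by "including as independent variables those that show significance in the univariate analysis or are of clinical interest". The 0.05 level applies to all tests. The text does not confine candidates to preoperative variables, and it does not say that technique stays in the model.

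On allocation, the Procedure part of section 7 says: "The assignment to one or another surgical technique will be made based on the criteria of the physician who diagnoses the patient".

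The same part lists two preoperative measurements, grip strength and BCTQ. Recorded at surgery are "Time of surgical intervention" and "Use or not of an ischemia cuff to perform surgery". Recorded at 2 weeks, 6 weeks and 3 months, among other items, is "Presence of pillar pain". Section 6 makes pillar pain a secondary outcome. Of the percutaneous route, section 4 says "it is expected that the incidence of discomfort and tenderness in the palmar area will be reduced". The questionnaire in Annex 1 opens with "How severe is your wrist or hand pain at night".

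**The concern.** Technique is not randomised, so any adjusted comparison depends on the covariates. Two things matter: the set should cover what drives the choice of technique, and it should contain nothing that technique itself may change. The stated rule secures neither. It selects on association with the outcome, and most of the variables the protocol lists are recorded at or after surgery.

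Pillar pain is the clearest case. It may be reduced by one technique, it is an outcome in its own right, and it plausibly feeds into a questionnaire that asks about hand pain. Holding it constant removes from the technique estimate whatever part of the effect runs through it. A real benefit can then be understated. If the techniques are equal overall, the adjusted result can show a difference in favour of open surgery that does not exist.

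Operative time and cuff use are weaker cases. They too are recorded after the choice, but the protocol does not say that they differ by technique or affect the BCTQ.

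**Working it through.** **Inputs from the protocol.** 98 per group, difference 0.94, SD 1, two-sided 0.05, 10% loss. Evaluable: 98 × 0.9 ≈ 88 per group, 176 in all. The stated inputs do not reproduce 98: 2 × (1.96 + 0.84)² / 0.94² gives 18 per group. That is a separate matter and this point does not rest on it. It does explain the second effect size used below: at SD 1 and 80% power, 0.40 needs 99 per group, so 0.40 is about what 98 per group can detect. It is not a protocol figure.

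**Assumed inputs.** Pillar pain 20%, 30% or 40% after open surgery against 10% percutaneous; own effect e of 0.5 or 1.0 BCTQ units; within-group SD 1. A variable enters only if its univariate p is below 0.05. Entry through clinical interest is not modelled.

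**Formula.** Let D be the total technique effect, positive when percutaneous is better. With pillar pain in the model, the technique coefficient estimates D − e × (open rate − percutaneous rate). For D = 0.40 and e = 0.5: 0.40 − 0.5 × 0.10 = 0.35, then 0.30 and 0.25.

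**Results by simulation** (open rate 20% / 30% / 40%; ranges cover separate runs):

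| D | e | Estimate with pillar pain in the model | Rejection rate |
|---|---|---|---|
| 0 | 0.5 | −0.05 / −0.10 / −0.15 | 5–6% / 9% / 12–14% |
| 0 | 1.0 | −0.10 / −0.20 / −0.30 | 10–11% / 28–29% / 52–53% |
| 0.40 | 0.5 | 0.35 / 0.30 / 0.25 | 65% / 50–51% / 36–37% |
| 0.40 | 1.0 | 0.30 / 0.20 / 0.10 | 55% / 29% / 11% |
| 0.94 | 0.5 | 0.89 / 0.84 / 0.79 | above 99% |
| 0.94 | 1.0 | 0.84 / 0.74 / 0.64 | at least 99% |

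Without pillar pain, power at 0.40 is 75%. At e = 0.5 pillar pain passes the screen in about 75% / 88% / 93% of studies when D is 0.40, and 84% / 96% / 99% when D is 0.94. Averages over all studies lie slightly closer to D than the table's estimates, because pillar pain sometimes fails the screen.

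**Hand check of one cell** (D = 0, e = 1.0, 40% v 10%). Mean within-group variance of pillar pain: (0.40 × 0.60 + 0.10 × 0.90) / 2 = 0.165. Residual SD: √(1 − 0.165) = 0.914. Squared correlation with technique: 0.15² / (0.165 + 0.15²) = 0.12. SE: 0.914 × √(2/88) / √0.88 ≈ 0.147. Then 0.30 / 0.147 ≈ 2.04, and the chance of exceeding 1.96 is about 53%, as simulated.

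**Variables with no effect of their own.** With groups g SD apart on operative time, the SE grows by √(1 + g²/4): 1.12, 1.41 and 1.80 for g = 1, 2, 3. Such a variable can pass the screen merely because it tracks technique.
- Operative time, g = 1 / 2 / 3: power at 0.40 falls from 75% to 69% / 53% / 36%; at 0.94 it is 92% or more. Rejection at D = 0 is 4.4% / 3.5% / 2.9%.
- Cuff use, 80% v 50%, 80% v 20%, 90% v 10%: power at 0.40 is 73% / 61% / 41%; at 0.94 about 95% or more.

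The harm here is essentially lost precision, and type I error is not inflated.

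**Missed confounders.** In an illustration with 196 patients and a confounder that steers the choice of technique but has a weak outcome effect (0.12 per SD), the screen dropped it in about 39% of runs. The average estimate moved only from about −0.20 to −0.21, so in this example the omission mattered far less than adjusting for pillar pain.

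**The case against.** Several objections have force.

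- **The harm is conditional.** The models must be used to compare techniques, and the analyst must offer a secondary outcome to the screen as a predictor. The text can also be read as a search for prognostic factors. A reader might infer that the plan will adjust for pillar pain, operative time and cuff use, or that technique will be left out. The protocol says neither; it only fails to rule them out.
- **At the protocol's own 0.94, power hardly suffers.** This stands. The large power losses arise at 0.40, and every rate and own effect is hypothetical. What remains at 0.94 is a biased estimate.
- **Covariate lists and the meaning of clinical interest usually belong in an SAP, which may exist.** Their absence is not the complaint. The significance screen is a rule the protocol does fix, and an SAP would inherit it.
- **Preoperative BCTQ might be screened out.** A reader might infer this, but it matters little. It is always kept in the runs if the outcome is a change score, and kept in 93% or more at a baseline-outcome correlation of 0.3. The clinical interest clause also permits keeping it.
- **The unadjusted t-test or Mann-Whitney comparison is untouched.** True of this mechanism, but with physician-chosen technique that comparison remains open to confounding and is no substitute.

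**Conclusion.** The point holds in a limited form. The protocol fixes a data-driven covariate rule that neither targets the reasons for choosing a technique nor excludes variables recorded after that choice. In a non-randomised comparison where regression is the only confounding control named, that is a poor rule.

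For pillar pain the consequence is bias, in either of two forms: a real percutaneous benefit understated, or a spurious advantage for open surgery when there is none. At an own effect of 0.5 the shift is 0.05 to 0.15 units over the assumed rates; at 1.0 it is 0.10 to 0.30. It would be wrong to conclude that every variable recorded after the choice inflates type I error, since one with no effect of its own does not. It would be equally wrong to say that type I error is safe throughout, since adjusting for pillar pain can raise it. Nor do the documents support treating operative time or cuff use as established pathways of the technique effect.

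The size rests on assumed rates and effects, and on the models being technique models. The change is worth making because it is cheap and bears on the main objective; nothing here shows that the study's conclusion would be overturned at 0.94.

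**What to change.** For the technique comparison, replace the screen with one model that always contains technique and a preoperative covariate set fixed before outcomes are seen and kept whatever the p-values. Use preoperative BCTQ and preoperative grip, both already collected, plus age, sex and EMG severity where the chart gives them. State that no intraoperative or postoperative variable enters this model. Report operative time and cuff use descriptively by technique, and analyse pillar pain as the secondary outcome it already is. Any search for prognostic factors becomes a separate model labelled exploratory.

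The cost is three or four sentences, a few degrees of freedom out of about 176 patients, and some chart extraction. Age, sex and EMG severity are not on the section 7 collection list. EMG confirmation is an inclusion criterion, but if the reports are not graded, severity has to be left out. Imbalances not foreseen in the fixed set would be handled only in a labelled sensitivity analysis.
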